Data generated from the RT-PCR assays (relative quantification (RQ) ratio, numerical value) will be presented as mean (standard deviation) for normally distributed data and as median [Interquartile range] for non-normally distributed data. P values will be reported as continuous numerical scales, with multiple testing adjustments. After performing the main analysis using a linear model specified a priori, various sensitivity analyses will be performed. These will include an analysis of residuals which will rely on graphical methods, examination of skewness, kurtosis, and other descriptive statistics. The sensitivity analyses may also include a Shapiro-Wilk test of the null hypothesis H_0 ‘the underlying distribution of the residuals is Gaussian’. The sensitivity analyses may also include assessment of the impact of using a modified version of the linear model analysis in which the scale of the dependent variable is transformed (e.g., log10 or some other Box-Cox transformation). The sensitivity analyses will be used only to guide our level of trust in the main results.

For the primary analysis, viral infectivity and viral load, we will first determine if these variables are normally distributed. However, we anticipate these variables to be right skewed. They will be log transformed if they are not normally distributed. We will then compare the demographic variables (age, race, sex, age and BMI) and groups (study arms). We will use Chi-square and ANOVA statistics to determine if the demographic variables are evenly distributed amongst the groups. If not we will adjust for these variables in subsequent analyses. In the rare event there are multiple demographic variables that are found to be significantly different by group we will create a propensity score to adjust for these variables in subsequent analyses.

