The primary analysis will be ANCOVA models with viral infectivity at time Post 0 minute, Post 1 minute, post 15 minute, post 30 minute, post 45 minute and post 60 minute adjusting for time Pre 0 minute. We will also perform a repeated measures analysis looking at viral infectivity over time, with the advantage of having one model with more power, while the ANCOVA model may give us a clearer answer if the rebound effect of viral infectivity is exponential. We will adjust for any demographic variables that are found to be significantly different between groups. We will adjust for any demographic variables that are found to be significantly different between groups.

The viral infectivity analysis will compare infectivity levels between mouth rinse types and across the time course for calculation of the reduction factor (RF calculated from PFU/mL, numerical value). The RF will be calculated as the difference in the quotient of the infection titre before (‘control titration’) and after the mouthrinse (‘remaining virus’). Therefore, the log10 titre and its (double) standard deviation (SD) were calculated as well as the variance of the RF.

Secondary Outcomes

Inflammation-associated cytokine and chemokine concentration (pg/mL) will be quantified using a Luminex bioanalyzer containing pre-validated internal standards of known concentration. Saliva and serum analyte concentrations will be compared between groups using descriptive statistics. Periodontal exam results will be reviewed to categorize patients’ periodontal status which will be reported as frequencies.

Tertiary Outcomes

The tertiary outcomes of this study are a periodontal exam and post-rinse surveys to evaluate patient perceptions of the mouthrinse, their symptoms and feedback on their willingness to use the product. Percentage of respondents will be gathered and reported for surveys. Periodontal exam data will be evaluated and the periodontal status for each participant will be assigned via the case definitions for periodontitis, gingivitis, and clinical periodontal health as described in the 2017 World Workshop

on the Classification of Periodontal and Peri-Implant Diseases and Conditions and the 2012 Centers for Disease Control and Prevention and American Academy of Periodontology case definitions.^{19, 20} Patients' final periodontal status will be the tertiary outcome of the periodontal exam and will be reported as the percentage of participants categorized into each diagnostic group.

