10.2 Sample Size and Randomization

Using data from Meiller *et al.* we calculated power at four time points.¹⁸ Time points included: Post-0 immediately after rinse, Post-30 (30 min post rinse), and Post-60 (60 min post rinse). In addition, we calculated a Post-45, which was the mid-point between 30 and 60 min in the Meiller *et al.* data. Based on this viral study evaluating mouth rinse efficacy against infectivity of Herpes Simplex Virus, an enveloped virus, power calculations were determined to estimate effect size and determine sample size as a function of length of mouth rinse time course.¹⁸ The sample size was justified by a paired t-test on outcomes between time points. With three simultaneous comparisons (t_1-t_0 , t_2-t_0 , t_3-t_0) over 30 min, an $n=16$ sample size can detect the effect size in Cohen's $d=0.7$, which is between medium and large, with 80% power and 0.016 type-I error rate by Bonferroni correction. Therefore, with four simultaneous comparisons (t_0-t_1 , t_0-t_2 , t_0-t_3 , t_0-t_4) the sample size required for each arm is ~25 participants per group to discern oral rinse efficacy at any given time point (minutes post rinse).

[name], who is the statistical consultant on this project, will create a block randomization schedule and perform these computations. SAS Institute (SAS Cary, NC) Proc PLAN will be used to create the randomization schedule. Block randomization will be used to ensure equal and random assignment into each study arm. All patients will be consented and then fill out our screening questions for inclusion and exclusion to confirm eligibility prior to being assigned to the randomization schedule. We will closely collaborate on [name] throughout all stages of this study to ensure statistical rigor.

The researcher responsible for collecting the salivary samples will be blinded to the mouthwash solution, as they will be given a pre-aliquoted mouthrinse in an unlabeled conical tube to provide to the patient for the rinse.

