10.5.3 Tertiary Outcomes

The tertiary outcomes of this study are a periodontal exam and post-rinse surveys to evaluate patient perceptions of the mouthrinse, their symptoms and feedback on their willingness to use the product. Percentage of respondents will be gathered and reported for surveys. Periodontal exam data will be evaluated and the periodontal status for each participant will be assigned via the case definitions for periodontitis, gingivitis, and clinical periodontal health as described in the 2017 World Workshop on the Classification of Periodontal and Peri-Implant Diseases and Conditions and the 2012 Centers for Disease Control and Prevention and American Academy of Periodontology case definitions.^{19, 20} Patients' final periodontal status will be the tertiary outcome of the periodontal exam and will be reported as the percentage of participants categorized into each diagnostic group. These tertiary outcomes are exploratory and therefore have no hypotheses assigned to them.

Table: Study Variables and Covariates

X Independent variables	Y Dependent variables for primary and secondary outcomes	Covariates
Mouthrinse Group	Viral infectivity (continuous positive variable)	Age (years)
Time (in minutes, 0, 15, 30, 45 and 60 minutes, visit 1 and 2)	Viral load (continuous positive variable)	Gender (m/f)
	Cytokine level (continuous positive variable)	Race (White, Native Hawaiian or other pacific islander, Asian, African American, Hispanic or Latino, American Indian or Alaska Native)
		BMI Body mass index (continuous range: 0-56)

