10.6 Data Analyses

qRT-PCR: Data will be presented as mean (standard deviation) for normally distributed data and as median [Interquartile range] for non-normally distributed data. P values will be reported as two tailed. Between group comparisons will be performed using a Student's T test or Mann-Whitney test. Normality will be assessed using the Kolmogorov-Smirnov test, and logistic regression will be performed with robust standard errors. Methods adapted from Bullard *et al* 2020.

Viral infectivity: The viral infectivity analysis will compare infectivity levels between mouth rinse types and across the time course for calculation of the reduction factor (RF). The RF will be calculated as the difference in the quotient of the infection titre before ('control titration') and after the mouthrinse ('remaining virus'). Therefore, the log₁₀ titre and its (double) standard deviation (SD) were calculated as well as the variance of the RF.

Inflammatory Markers: Inflammation-associated cytokine and chemokine concentrations (IL-6, CXCL-10, IL-8, and IL-10 [pg/mL]) will be quantified from saliva and blood samples collected at each visit and across the salivary collection time course using multiplex analyte analysis (Luminex technology) and using internal, manufacturer supplied standards of known concentration (pg/mL).

The analysis plan will include use of sensitivity analyses to evaluate the robustness/fragility of the study's main results to reasonable perturbations of the statistical methods and assumptions used in the main analysis. We will first describe the demographics (age, race, sex and BMI) for each study arm. If significant differences are found between groups, we will adjust the remainder of the analysis. The main analysis will be a repeated measures linear regression model(s). If multiple demographics are found to be significantly different the propensity scores will be created and final models will be adjusted by propensity scores. In the primary analysis, viral load and replication as measured by changes in genomic, strand, and subgenomic expression, will be evaluated and compared between treatment groups. Repeated measures linear regression models will be utilized to look at changes in viral load logarithmically before and after treatment. Similarly,

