in the secondary analyses, the repeated measures linear regression will be used to compare the changes in other continuous outcomes (such as immunological parameters) from baseline to specific time points outlined. Statistical significance will be tested using a two-sided 0.05 level with adjustments for multiple testing. Multiple testing correction will be made by Tukey adjustments (for multiple study arms) and False Discovery Rate (FDR) where appropriate (i.e. multiple inflammatory markers).

All statistical estimates of population parameters will be tabulated along with corresponding confidence intervals (CIs) and/or standard errors (SEs) to convey level of precision. All P- values will be reported as continuous numerical outputs (and not as dichotomous results). All hypothesis tests yielding large p-value (e.g., $p > \alpha$) will be reported as being inconclusive.

Power Calculation: Using data from Meiller *et al.* we calculated power at four time points.¹⁸ Time points included: Post-0 (immediately post rinse), Post-30 (30 min post rinse), and Post-60, (60 min post rinse). In addition, we calculated a Post-45, which was the midpoint between 30 and 60 min in the Meiller *et al.* data. Based on this viral study evaluating mouth rinse efficacy against infectivity of Herpes Simplex Virus, an enveloped virus, power calculations were determined to estimate effect size and determine sample size as a function of length of mouth rinse time course.¹⁸ The sample size was justified by a paired t-test on outcomes between time points. With three simultaneous comparisons (t_1-t_0 , t_2-t_1 , t_2-t_0) over 30 min, an $n=16$ sample size can detect the effect size in Cohen's $d=0.7$, which is between medium and large, with 80% power and 0.016 type-I error rate by Bonferroni correction. Therefore, with four simultaneous comparisons (t_0-t_1 , t_0-t_2 , t_0-t_3 , t_0-t_4) the sample size required for each arm is ~25 participants per group to discern oral rinse efficacy at any given time point (minutes post rinse).

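### Sections 10.2 and 10.6 name different primary analyses, one includes a time that is never sampled, and no multiplicity method is assigned to time points or to the two primary measures

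*Combined protocol and SAP*

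**What the plan says.** Section 10.2 Research Hypotheses, under Primary Outcomes, gives the lead role to a set of per-time models: "The primary analysis will be ANCOVA models with viral infectivity at time Post 0 minute, Post 1 minute, post 15 minute, post 30 minute", then 45 and 60 minutes, each adjusted for the pre-rinse value. A repeated-measures analysis of infectivity is offered there as an addition. The same subsection treats two measures as primary: "For the primary analysis, viral infectivity and viral load, we will first determine if these variables are normally distributed".

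Section 10.6 Data Analyses reads differently: "The main analysis will be a repeated measures linear regression model(s"). It goes on: "In the primary analysis, viral load and replication as measured by changes in genomic, strand, and subgenomic expression" will be compared between groups. For RT-PCR it also lists a "T test or Mann-Whitney test. Normality will be assessed using the Kolmogorov-Smirnov test".

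The variables table in section 10.5.3 gives the sampled times: "Time (in minutes, 0, 15, 30, 45 and 60 minutes, visit 1 and 2"). The sampling descriptions in sections 2.2, 3, 5.1 and 6.2 agree.

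On multiplicity, section 10.6 promises adjustment at a two-sided 0.05 level and names its methods: "Multiple testing correction will be made by Tukey adjustments (for multiple study arms"), and FDR where appropriate, with inflammatory markers as the case given. The sample-size text works with other comparisons: "The sample size was justified by a paired t-test on outcomes between time points", Bonferroni-corrected over the time comparisons.

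Section 10.4 runs infectivity assays on samples at 0 minutes, which it labels baseline, and at 30 minutes, and only where the Ct is 22 or lower. Section 3 (sample processing) and section 11.3.3 speak of all samples.

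**The concern.** A reader cannot tell which single result answers the primary question. The lead model, the lead measure and the set of time points all change between current sections. Section 10.5 says that the committee judging which rinse is more effective will not be masked to group, so the choice among competing primary results could follow the data.

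Two further points bear on the same result. First, the sizing controlled error over time points, but the analysis text assigns no method to them or to the pair of primary measures. Second, the Ct 22 rule in sections 3 and 10.4 applies to samples, including post-rinse ones. If a post-rinse sample above the cut-off is not assayed, and is then excluded as missing under section 3, a rinse that lowers RNA could lose its best responses from the infectivity outcome.

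**Working it through.** **Passages side by side**

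| Item | 10.2, Primary Outcomes | 10.6 | 10.4 |
|---|---|---|---|
| Lead model | separate ANCOVAs, one per time | repeated-measures regression; t-test or Mann-Whitney also listed for RT-PCR | none named |
| Measure | infectivity in the ANCOVA sentence; infectivity and viral load just before it | RNA load and replication | both |
| Post-rinse times | 0, 1, 15, 30, 45, 60 min | not listed | 30 min, plus a 0 min labelled baseline |

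Samples exist pre-rinse and at 0, 15, 30, 45 and 60 minutes, so the 1-minute ANCOVA has no data. The definitions table and section 6.2.2 define baseline as pre-rinse, whereas T_0 in section 3 is post-rinse, so 0 min in section 10.4 is ambiguous. If section 10.4 governs the final assays, the ANCOVAs at 15, 45 and 60 minutes have no data either.

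**The plan's own multiplicity figure.** Three comparisons give 0.05/3 = 0.0167 (stated as 0.016); four imply 0.05/4 = 0.0125. A paired t-test with d = 0.7, two-sided 0.0125 and 80% power needs n = 26 by exact noncentral t, and n = 25 gives 78%. So the figure of about 25 per arm is consistent with Bonferroni over four within-arm time comparisons. (The stated n = 16 at 0.016 does not reproduce: exact t needs 25. That is a separate sizing matter, and this point does not depend on it.)

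**Error rate if nothing is applied over time.** Inputs from the plan: 5 arms of 25, five post-rinse times, Tukey 5% over arms. Degrees of freedom are 5 × 25 − 5 = 120 and the critical t is 2.77. The documents give no correlation between times, so equal correlations of 0 to 0.9 are assumed. Simulation with no arm effect gives the chance of at least one false finding:

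| Five times | 0 | 0.5 | 0.8 | 0.9 |
|---|---|---|---|---|
| Any of the 10 arm contrasts | 22.5% | 19.2% | 13.5% | 10.9% |
| Any rinse v water, either direction | 11.1% | 9.4% | 6.8% | 5.2% |
| Any rinse falsely better than water | 5.9% | 4.7% | 3.5% | 2.6% |
| Same rinse better at 0, 15 and 30 min | 0.0% | 0.0% | 0.2% | 0.4% |

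Exact check under independence: 1 − 0.95^5 = 22.6%.

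**If only 30 minutes is assayed but both measures are primary** (correlation between measures assumed over the same range): 9.9%, 9.4%, 8.1% and 7.2% over all contrasts; 4.6%, 4.4%, 3.8% and 3.4% for rinse v water in either direction. One measure at one time gives 5.0% over all contrasts.

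**Precision of a single 30-minute contrast.** The detectable difference at 80% power is roughly (2.77 + 0.84) × √(2/25) = 1.02 residual SD at 25 per arm. The noncentral t gives 1.02, and 1.15 and 1.33 at 20 and 15 per arm (assumed numbers). With Tukey at 2.5% and 25 per arm it is 1.10.

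**The hypothesised 20% reduction on the RF scale.** RF = log10(pre/post) = log10(1/0.8) = 0.097.

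**The case against.** Infectivity and RNA are both declared primary in sections 1.1, 10.2 and 10.5.1, so the RNA sentence in section 10.6 can be read as covering one half of a declared pair. A reader might infer that the primary outcome was switched from infectivity to RNA; the documents do not support that. The conflict over the lead model and the unsampled time remains.

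A reader might also infer that multiplicity is ignored and that the trial runs a 23% false-positive risk. Sections 10.2 and 10.6 both promise adjustment, so the gap is an unassigned method, not a refusal. The 23% further needs independent saliva samples 15 minutes apart, nothing applied over time, and rinse-v-rinse contrasts counted. For the efficacy claim, a rinse falsely better than water, the range is about 3% to 6%. It is under 1% if persistence to 30 minutes is read as winning at each time up to then. Section 10.6 also reports confidence intervals and continuous p-values. All of this stands, and it puts inflation second.

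Section 10.4 is headed as stopping rules and describes batch analyses, so its 0- and 30-minute limit may not govern the final assays. That is possible, but nothing says so.

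Finally, a reader might infer that the best responders will be dropped. Section 3 attributes missing data to uncompleted visits or insufficient saliva, and no passage says how samples above Ct 22 are analysed. The loss is a conditional risk, not a stated rule.

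**Conclusion.** The point holds, chiefly because the primary result is undefined. Current sections disagree on the lead model. They are unclear on how the two primary measures rank. They list a time that is never sampled, and they leave open which times have infectivity data at all. Neither time points nor the pair of measures has an assigned multiplicity method, although the sample size was built on Bonferroni over time.

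The inflation is secondary and depends on the reading. It is about 23% to 11% over all ten contrasts at five times, 11% to 5% for any rinse v water in either direction, and 6% to 3% for a rinse falsely better than water. With both measures at 30 minutes only, it is about 10% to 7% over all contrasts and 5% to 3% for rinse v water. These figures rest on assumed correlations of 0 to 0.9, 25 analysable participants per arm, and Tukey at 5% for each time or measure with nothing further. The Ct 22 loss cannot be sized from the documents.

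**What to change.** 1. In sections 10.2 and 10.6 name one primary analysis: log10 infectivity at 30 minutes post-rinse, the time in the trial's own hypothesis, compared between arms with adjustment for the pre-rinse value and Tukey over arms. If several post-rinse times are assayed, make this the 30-minute contrast of one repeated-measures model; if only 30 minutes is assayed, use a single ANCOVA.
2. Label the other times secondary. Make RNA load secondary, with the same model in place of the t-test and Mann-Whitney text. If RNA stays primary and success on either measure suffices, assign 2.5% to each; no split is needed if both must succeed.
3. Report each arm's mean RF at 30 minutes with its confidence interval against 0.097. This is a within-arm quantity and should not be compared with the between-arm contrast.
4. Delete the 1-minute time, replace the 0-minute baseline label in section 10.4 with pre-rinse, and reconcile that section with sections 3, 10.2 and 11.3.3 on which times are assayed.
5. Apply the Ct 22 cut-off to the pre-rinse sample only and assay that participant's post-rinse samples whatever their Ct. Set in advance how zero or below-limit plaque counts enter the log10 analysis, for example as left-censored at the assay limit. Without such a rule the logarithm is undefined for the best responses.

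Cost: mostly wording, plus some added assays. Other times lose primary status, as does RNA unless kept; keeping it at 2.5% raises the detectable difference at 25 per arm from 1.02 to 1.10 residual SD. Requiring a pre-rinse Ct of 22 or lower may leave fewer than 25 analysable per arm, with detectable differences of 1.15 at 20 and 1.33 at 15. The plan should state the number expected.

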10.2 Sample Size and Randomization

Using data from Meiller *et al.* we calculated power at four time points.¹⁸ Time points included: Post-0 immediately after rinse, Post-30 (30 min post rinse), and Post-60 (60 min post rinse). In addition, we calculated a Post-45, which was the mid-point between 30 and 60 min in the Meiller *et al.* data. Based on this viral study evaluating mouth rinse efficacy against infectivity of Herpes Simplex Virus, an enveloped virus, power calculations were determined to estimate effect size and determine sample size as a function of length of mouth rinse time course.¹⁸ The sample size was justified by a paired t-test on outcomes between time points. With three simultaneous comparisons (t_1-t_0 , t_2-t_0 , t_3-t_0) over 30 min, an $n=16$ sample size can detect the effect size in Cohen's $d=0.7$, which is between medium and large, with 80% power and 0.016 type-I error rate by Bonferroni correction. Therefore, with four simultaneous comparisons (t_0-t_1 , t_0-t_2 , t_0-t_3 , t_0-t_4) the sample size required for each arm is ~25 participants per group to discern oral rinse efficacy at any given time point (minutes post rinse).

[name], who is the statistical consultant on this project, will create a block randomization schedule and perform these computations. SAS Institute (SAS Cary, NC) Proc PLAN will be used to create the randomization schedule. Block randomization will be used to ensure equal and random assignment into each study arm. All patients will be consented and then fill out our screening questions for inclusion and exclusion to confirm eligibility prior to being assigned to the randomization schedule. We will closely collaborate on [name] throughout all stages of this study to ensure statistical rigor.

The researcher responsible for collecting the salivary samples will be blinded to the mouthwash solution, as they will be given a pre-aliquoted mouthrinse in an unlabeled conical tube to provide to the patient for the rinse.

The PI, Co-I, study coordinators and study personnel who work for GoHealth are authorized to break the blinding if a patient suffers an allergic or adverse reaction to one of the mouthrinses. Though highly unlikely, as all proposed mouth rinses are commercially available over the counter, adverse or allergic reactions are possible. Using the numerical code associated with the participant and mouthrinse syringe, the study personnel can reference the block randomization schedule to determine the mouthrinse type, to inform the emergency medical workers, poison control or the emergency room what type of mouthrinse product led to the reaction.

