The primary objective of this study is to determine the efficacy of antiseptic mouthwashes on reducing SARS-CoV-2 cellular infectivity in COVID+ patient saliva. *We hypothesize that SARS-CoV-2+ patients will have a >20% reduction in SARS-CoV-2 viral infectivity following a 60 second oral rinse with an antiseptic mouthrinse and that this reduction will persist for at least 30 minutes.* This primary objective will focus on quantifying SARS-CoV-2 viral infectivity (Reduction Factor (RF) calculated from plaque forming units [PFU] / mL) and viral titer (Relative Quantification (RQ) ratio) using an *in vitro* infectivity assay and RT-PCR. This objective provides urgently needed data to guide healthcare workers on the proper use of specific commercially available mouthwashes capable of reducing SARS-CoV-2 viral infectivity and potentially limiting SARS-CoV-2+ transmission.

1.2 Secondary Objective:

The secondary objectives are to measure cytokine and chemokine levels (pg/mL) in samples taken from SARS-CoV-2+ patients and also to determine the frequency of periodontal disease among SARS-CoV-2+ patients. *We hypothesize that SARS-CoV-2+ patients using Colgate oral health products will have lower inflammatory marker levels than controls. Furthermore, we hypothesize that SARS-CoV-2+ patients will have a greater incidence of periodontal disease than the general population.*

1.3 Tertiary Objective (*Exploratory*):

The tertiary objective of this study is to use post-rinse surveys to evaluate patient perceptions of the mouthrinse and feedback on their willingness to use the product (units: percentage of respondents). Additionally, a periodontal exam will be performed to assess periodontal health. Patients' final periodontal status will be the tertiary outcome of the periodontal exam and will be reported as the percentage of participants categorized into each diagnosis. This tertiary outcome is exploratory.

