10.2 Research Hypotheses

The central hypothesis of this study is that COVID-19+ patients will have a >20% reduction in SARS-CoV-2 viral infectivity following oral rinse with an antiseptic mouthrinse and that this reduction will persist for at least 30 minutes.

The secondary hypothesis is that COVID-19+ patients using Colgate oral health products will have lower inflammatory marker levels than controls. Furthermore, we hypothesize that COVID-19+ patients will have a greater incidence of periodontal disease than the general population.

Sample Size Considerations

Using data from Meiller *et al.* we calculated power at four time points.¹⁸ Time points included: Post-0 immediately after rinse, Post-30 (30 min post rinse), and Post-60 (60 min post rinse). In addition, we calculated a Post-45, the midpoint between 30 and 60 min, in the Meiller *et al.* data. Based on this viral study evaluating mouth rinse efficacy against viral infectivity of Herpes Simplex Virus, an enveloped virus, power calculations were determined to estimate effect size and determine sample size as a function of length of mouth rinse time course.¹⁸ The sample size was justified by a paired T-test on outcomes between time points. With three simultaneous comparisons (t_1-t_0 , t_2-t_0 , t_2-t_1) over 30 min, an $n=16$ sample size can detect the effect size in Cohen's $d=0.7$, which is between medium and large, with 80% power and 0.016 type-I error rate by Bonferroni correction. Therefore, with four simultaneous comparisons (t_1-t_0 , t_2-t_0 , t_2-t_1 , t_3-t_0) the sample size required for each arm is ~25 participants per group to discern oral rinse efficacy at any given time point (minutes post rinse).

Statistical analysis of our data will be performed by [name], the statistician on this project. Statistical analysis of our data will be performed by [name], the statistician on this project. [name] will be involved in all stages of this project to help ensure statistical rigor.

Primary Outcomes

The analyses will compare viral titre (RT-PCR) and viral infectivity levels between mouth rinse types and across the time course.

Table: Variable Types for Primary Outcomes

	Viral Infectivity (Continuous)	Viral Load (Continuous)
Age, Years (Continuous)		
Race (Categorical)		
Sex (Categorical)		
BMI (Continuous)		
Time (Categorical)		
StudyGroup (Categorical)		

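### The n=16 power statement gives about 55%, not 80%, if d is the standardised paired difference, and the target of about 25 per arm cannot be derived from it

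*Combined protocol and SAP*

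**What the plan says.** The sample-size argument appears four times: in section 2.2, under Sample Size Considerations in section 10, in section 10.2 (Sample Size and Randomization), and in the Power Calculation paragraph of section 10.6. The listed contrasts differ somewhat between these places, but the number of comparisons, n, d, power and alpha are the same throughout.

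- The test is within-patient: "The sample size was justified by a paired t-test on outcomes between time points".
- For three comparisons over 30 minutes, with a Bonferroni type-I error of 0.016, the plan says that "an $n=16$ sample size can detect the effect size in Cohen's $d=0.7$, which is between medium and large, with 80% power".
- It then moves, by the word Therefore, to four comparisons: "the sample size required for each arm is ~25 participants per group to discern oral rinse efficacy at any given time point". No d, alpha or power is restated for that second figure.

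The effect is said to be informed by a cited study of a mouth rinse against herpes simplex virus. The plan does not say whether d is standardised by the SD of the paired difference or by the raw SD, and it gives no pre/post correlation. The sample-size paragraph does not state sidedness; section 10.6 sets a two-sided 0.05 level with multiplicity adjustment.

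The primary hypothesis in section 1.1 is a within-patient one: "SARS-CoV-2+ patients will have a >20% reduction in SARS-CoV-2 viral infectivity following a 60 second oral rinse". The planned analysis also compares arms: "The analyses will compare viral titre (RT-PCR) and viral infectivity levels between mouth rinse types and across the time course". For this the Primary Outcomes text says "The primary analysis will be ANCOVA models with viral infectivity at time Post 0 minute", adjusted for the pre-rinse value, and adds "We will also perform a repeated measures analysis looking at viral infectivity over time, with the advantage of having one model with more power". Section 10.6 names repeated-measures regression as the main analysis, with Tukey adjustment across arms.

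**The concern.** A paired test with 16 pairs and a moderate-to-large standardised difference would not be expected to reach 80% power once alpha has been cut to about a third of 0.05. The step from 16 to about 25 also looks too large for one extra Bonferroni comparison. This argument is the only stated basis for the size of each arm, so a reader who cannot reproduce it cannot tell which effect the trial was designed to detect. A reader may also take the 80% as covering the comparison of each rinse with water, which a within-arm paired test does not address.

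**Working it through.** **Inputs.** From section 10.2 (Sample Size and Randomization): paired t-test, d=0.7, n=16, alpha 0.016, 80% power, about 25 per arm. From section 10.6: two-sided testing. Derived: 0.05/3 = 0.0167 (printed as 0.016) and 0.05/4 = 0.0125 for four comparisons; the plan does not print the latter.

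**Formula.** Power = P(|T| > c), where T is noncentral t with n − 1 degrees of freedom and noncentrality d_z × √n, c is the critical value, and d_z is the mean paired difference divided by the SD of that difference.

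**Step 1. The plan's own figure, with d = d_z = 0.7.** Noncentrality is 0.7 × √16 = 2.80. The two-sided critical value at 0.016 on 15 df is 2.714. Power is 54.8%. Using 0.0167 gives 55.5%. One-sided at 0.016 (critical value 2.364) gives 66.9%. The stated 80% is not reproduced.

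**Step 2. What would give 80%.**

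| n | d_z | alpha (two-sided) | Power |
|---|---|---|---|
| 16 | 0.70 | 0.016 | 54.8% |
| 25 | 0.70 | 0.016 | 81.0% |
| 25 | 0.70 | 0.0125 | 78.0% |
| 26 | 0.70 | 0.0125 | 80.1% |
| 16 | 0.90 | 0.016 | 80% |

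On this scale 80% needs 25 pairs for three comparisons and 26 for four, a difference of one.

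**Step 3. A possible origin of 16.** Without the Bonferroni correction, the normal approximation at two-sided 0.05 gives n = (1.960 + 0.842)² / 0.7² = 16.02. This is a guess at the source, since the documents do not show the calculation. The exact t-test at 0.05 with n=16 has 74.5% power.

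**Step 4. d on the raw SD.** With equal pre and post SDs and correlation ρ, d_z = 0.7 / √(2(1 − ρ)).

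| Assumed ρ | d_z | Power, n=16, alpha 0.016 | n for 80% at 0.016 | n for 80% at 0.0125 |
|---|---|---|---|---|
| 0 | 0.495 | 26.9% | 47 | 49 |
| 0.5 | 0.700 | 54.8% | 25 | 26 |
| 0.7 | 0.904 | 80.2% | 16 | 17 |
| 0.8 | 1.107 | 94.2% | 12 | 13 |

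At ρ of about 0.7 the n=16 statement is correct, but four comparisons then need 17. In the rows that bracket the plan's figures (ρ 0.5 to 0.8), the fourth comparison adds one participant; even at ρ = 0 it adds two.

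**Step 5. Between-rinse power.** None is stated. To show how far it depends on missing inputs, take ANCOVA with 25 per arm, five arms, one time point, no change on water, d=0.7 in raw SDs, 125 − 5 − 1 = 119 df and a Tukey critical value of 2.770. Noncentrality is 0.7 / √(1 − ρ²) × √(25/2). Power is 38.8% at ρ = 0 and 99.8% at ρ = 0.9. The effect, the correlation and the application of the Tukey adjustment to the ANCOVA are all assumed here, so this says nothing about the trial's actual power.

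**The case against.** The strongest reply is that d is undefined, so 55% is one convention among several. On the raw-SD scale power at n=16 runs from 27% to 94% over correlations 0 to 0.8, and at about 0.7 it is the stated 80%. This stands: the 55% and any replacement figures are conditional on d being the paired difference.

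A reader might also infer that no reading supports both 16 and about 25. That goes too far. The plan says sample size was considered in relation to the length of the time course, and the second sentence restates no d. With d=0.7 in raw SDs, a correlation of 0.70 gives 80.2% at n=16 and 0.016, while a correlation of 0.52 gives 79.9% at n=25 and 0.0125. A correlation that weakens over a longer course could therefore fit both. Nothing in the documents says this was done, and the stated reason for the increase is the number of comparisons, so the inference as written remains unsupported.

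The reply can fairly add that n=16 is an intermediate figure that no arm uses. The target of 25 complete datasets, from 30 enrolled per arm, has 78% to 81% power for the within-patient test at d_z = 0.7.

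**Conclusion.** The concern holds in this form. With d as the standardised paired difference and two-sided testing, n=16 at 0.016 has about 55% power, not 80%. The figure of about 25 per arm is approximately right when computed directly from d=0.7, but it is not a consequence of the n=16 statement: with d and the correlation fixed, the fourth comparison adds about one participant, whereas the plan adds nine (25 − 16).

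Two stronger conclusions are tempting and not supported. The first is that the trial has only 55% power for its within-patient hypothesis; the arms are planned at 25, not 16. The second is that the rinse comparison is underpowered. The plan gives no between-arm effect, correlation, or number expected to be evaluable for infectivity after the cycle-threshold cut-off of 22 (sections 3 and 10.4), and plausible assumptions lead to very different answers. Section 10.4 also provides for tighter enrolment if samples from days 6 to 7 routinely lack virus. What can be said is that the stated power does not extend to that comparison.

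This should be fixed, but it does not put the planned arm size for the within-patient test in doubt.

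**What to change.** In all four places (section 2.2, Sample Size Considerations in section 10, section 10.2 Sample Size and Randomization, and the Power Calculation in section 10.6):

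1. Define d, either as the mean paired difference over the SD of that difference, or on the raw SD with the assumed pre/post correlation stated.
2. Restate n, alpha, sidedness and power consistently for three and for four comparisons, using one list of contrasts.
3. If d is the paired difference, replace the n=16 statement with n=25 for 80% power at 0.016 (or keep n=16 with d of about 0.90), and give 78% power at n=25 for four comparisons at 0.0125. If d is on the raw SD, give the correlation used for each figure and explain why about 25 is needed.
4. State that this power applies to the within-arm pre/post test and not to the between-rinse ANCOVA or repeated-measures comparison, for which the plan states no power.

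Adding a between-rinse power figure is optional. It would need the sponsor to supply the effect scale, the correlation and the number evaluable per arm after the cycle-threshold cut-off.

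The cost is text only, with no added participants and no change to the planned analysis.
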